1.0 Objectives

1.1 Purpose:

This is a randomized, double-blind, placebo-controlled clinical trial to compare Vitamin C versus placebo for patients presenting to the ICU with a diagnosis of septic shock.

Specific Aim 1: Determine if patient survival is improved with the use of Vitamin C.

Hypothesis Aim 1: Compared to placebo, moderate-dose Vitamin C will improve survival.

Specific Aim 2: Determine whether Vitamin C improves secondary clinical outcomes including but not limited to: duration of vasopressor therapy, duration of ICU stay, lactate clearance, and organ failure.

Hypothesis Aim 2: Compared to placebo, moderate-dose Vitamin C will improve clinical outcomes.

Specific Aim 3: Identify individual and clinical characteristics associated with responses to Vitamin C.

Hypothesis Aim 3: Specific characteristics exist that can identify those with a greater chance for a therapeutic response.

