- i. Total intravenous fluid administered from presentation until various intervals (3 hours, 6 hours, and 24hours), until resolution of shock, and from Vitamin C (or placebo) administration until resolution of shock.
- j. Effect of standard of care medications including corticosteroids as a sub-group analysis.

Outcome endpoint for Specific Aim 3: In general, clinical and biochemical characteristics associated with Vitamin C responsiveness will be examined. Specifics include:

- a. Assessment of whether time from onset of septic shock to receipt of Vitamin C (or placebo) influences effectiveness of Vitamin C therapy.
- b. Treatment effects as associated with or without initial presentation of inflammatory response

- Fever versus hypothermia
- Leukocytosis versus leukopenia
- Surgical versus medical source control
- c. Biobanking of blood specimens for future assessment of:
 - Vitamin C levels
 - Cytokine and chemokine levels
 - Danger associated molecular patterns (DAMPs)
 - Markers of necroptosis (RIP1 and RIP3)
 - Mitochondrial DNA and RNA for gene expressions
 - Genetic features favorable to Vitamin C therapy

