5.0 Procedures Involved

5.1 Study Design:

This is a multi-site, randomized, double-blind, placebo-controlled trial comparing a regimen of moderate-dose (6000 mg per day) Vitamin C supplementation versus placebo for the treatment of patients presenting to the ICU with septic shock. Both groups will continue to receive all other standard of care measures for septic shock as clinically indicated. Groups will be enrolled and receive study drug/placebo for 4 days (96 hours) or until 24 hours post-last pressor dose, whichever is sooner.

5.2 Study Procedures:

When a potentially eligible participant is identified, the PI or other clinical research team member will approach the individual with floor staff permission and coordination to explain the research.

PROTOCOL TITLE: Evaluating Vitamin C in Septic Shock: A Randomized Double Blind Control
Trial

VERSION DATE: March 17, 2020

After signing the consent and completing eligibility procedures, IDS will be notified. IDS will perform randomization and dispense appropriate study drug/placebo infusion materials.

Infusions must be started within 24 hours post-presentation of septic shock. Those participants who consent but cannot start an infusion within 24 hours will still follow all research procedures related to data collection except for banking of biospecimens.

Participants randomized to Vitamin C will receive IV parenteral Vitamin C; with a 1000 mg bolus to start and followed by a continuous infusion at 250 mg/hr for four days or off pressors for 24 hours, whichever is sooner. Placebo will be given as a matched infusion on the same schedule.

Chart review will take place at 24 hour time periods (Day 0, 1, 2, 3, and 4).

Blood draws for biobanking will occur at Day 0, 1, and 3 (0, 24 and 72 hours), 25 mL on day 0, and then 20 mL on days 1 and 3. Patients discharged from the hospital will not undergo blood draws following discharge. Those still in the hospital, any floor or unit, will have blood drawn if clinically possible. Blood draw will be based on a convenience sample only. Blood draw will only be done when study clinician is available and when time is available for processing and transporting. Not all participants will have all, or any, blood draw done for biobanking.

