16.0 Data Management

16.1 Data Analysis Plan:

Patient baseline characteristics will be summarized and presented using means and standard deviations for continuous variables and frequencies and percentages for categorical variables. Treatment groups will be compared using two-sample t test for continuous variables and Chi-square test for categorical variables.

Analysis plan for Aim 1: Mortality rates between treatment groups will be compared using Chi-square test. Logistic regression model will be used to model the probability of death. Model will include treatment group and covariates determined by the investigators to impact mortality and/or those that are significantly different between groups at baseline.

Analysis plan for Aim 2: Clinical outcomes at ICU discharge will be compared between groups using two-sample t test for continuous variables and Chi-square test for categorical variables. Multivariate linear and logistic regression analysis will be performed for continuous outcomes and dichotomous outcomes respectively to adjust for covariates.

Analysis plan for Aim 3: Correlation analysis will be conducted to examine the association between clinical characteristics and Vitamin C responsiveness.

Intention-to-treat analysis will be used. Analysis will be performed using Statistical Analysis Software (version 9.3, SAS Institute Inc., Cary, NC).

16.2 Power Analysis:

The trial will enroll enough participants to demonstrate a 20% mortality difference in between treatment groups. Based on this information, 124 patients, 62 patients in each arm, would be needed to have an 80% power to detect a 20 % decrease in hospital mortality between the two groups with a two-tailed alpha error of 0.05. To account for potential dropout of participants, planned enrollment will be 70 per arm, 140 total.

16.3 Data Integrity:

REDCap™ data will be periodically reviewed by the regulatory specialist and project manager or coordinator; to occur at the request of the PI and before final analysis occurs. Standard data quality checks will be run using REDCap™'s integrated programs.

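### Aim 3 correlates characteristics with an undefined responsiveness to vitamin C, but its questions concern effect modification and no treatment-by-characteristic interaction is planned

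*Combined protocol and SAP*

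**What the plan says.** The Aim 3 hypothesis (section 1.1) is that "Specific characteristics exist that can identify those with a greater chance for a therapeutic response".

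Section 3.2 turns this into specific questions. Item a is "Assessment of whether time from onset of septic shock to receipt of Vitamin C (or placebo) influences effectiveness of Vitamin C therapy". Item b is "Treatment effects as associated with or without initial presentation of inflammatory response", with three contrasts beneath it: "Fever versus hypothermia", high against low white cell count, and surgical against medical source control. Item c is "Biobanking of blood specimens for future assessment of" several laboratory markers. It is left aside here because it concerns later work and, under section 5.2, "Blood draw will be based on a convenience sample only".

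The whole analysis plan for Aim 3 is one sentence in section 16.1: "Correlation analysis will be conducted to examine the association between clinical characteristics and Vitamin C responsiveness". Section 3.2 also uses the term responsiveness, but neither section defines it.

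The Aim 1 model in section 16.1 names treatment and covariates. The Aim 2 models adjust for covariates. The only other subgroup provision is item j under Aim 2 in section 3.2: "Effect of standard of care medications including corticosteroids as a sub-group analysis". None of these mentions an interaction.

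**The concern.** Items a and b ask how the difference between vitamin C and placebo changes with a characteristic. Item a names both arms, and item b speaks of treatment effects. The method in section 16.1 relates a characteristic to a quantity that is undefined and that cannot be observed in any one patient: nobody's outcome is seen both with and without the drug.

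The nearest analysis that could be programmed is a correlation of each characteristic with a clinical outcome. That finds patients who do well or badly, whatever they were given. Time to treatment, temperature and white cell count may plausibly be prognostic in septic shock. The trial could then report a prognostic factor as a marker of drug response even if the drug does nothing.

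**Working it through.** **1. What each analysis estimates.** Let p(C,1) and p(C,0) be mortality on vitamin C with and without a characteristic, and p(P,1) and p(P,0) the same on placebo.

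- Effect modification: [p(C,1) − p(P,1)] − [p(C,0) − p(P,0)].
- Rearranged: [p(C,1) − p(C,0)] − [p(P,1) − p(P,0)].
- Correlation within the vitamin C arm reflects only p(C,1) − p(C,0), which is the effect modification plus the prognostic difference seen on placebo.
- Correlation pooled over two equal arms reflects the average of the two within-arm differences.

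Neither correlation is zero when the characteristic is prognostic and the drug is inert.

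**2. Inputs.** From the documents: 62 per arm, 124 in total, two-sided 0.05 (section 16.2); mortality 25%-50% (section 2.1). Assumed: factor strength, factor prevalence, and death as the outcome.

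Section 16.2 gives no figure for Aim 3 and no control rate. Its 62 per arm is reproduced for Aim 1 if 30% versus 10% is assumed: (1.96·√(2·0.2·0.8) + 0.8416·√(0.21 + 0.09))² / 0.20² = 61.6, rounded up to 62. Here 62 and 124 serve only as the available sample.

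**3. Hand check of one case.** Suppose mortality is 20% without and 40% with a 50%-prevalence factor, in both arms, with no drug effect. The odds ratio is (0.40/0.60)/(0.20/0.80) = 2.67. In the vitamin C arm, with 31 patients per level:

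- SE = √((0.16 + 0.24)/31) = 0.114.
- z = 0.20/0.114 = 1.76.
- Chance of p<0.05 ≈ Φ(1.76 − 1.96) = 42%.

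Simulation of this case gives 40%. The both-arm interaction test rejects in 5.5%.

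**4. Simulation.** 40,000 trials per setting, no drug effect and no effect modification. Entries are the share of trials with p<0.05 at 50% prevalence, by overall mortality.

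| Analysis | Prognostic OR | 25% | 30% | 40% | 50% |
|---|---|---|---|---|---|
| Correlation, vitamin C arm (62) | 2 | 20.4% | 23.0% | 26.1% | 27.5% |
| Correlation, vitamin C arm (62) | 3 | 43.1% | 48.0% | 54.8% | 57.2% |
| Correlation, pooled (124) | 2 | 37.3% | 41.6% | 46.8% | 48.7% |
| Correlation, pooled (124) | 3 | 73.2% | 78.3% | 83.7% | 85.6% |

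The Wald interaction test rejects in 3.8%-5.3% for odds ratios 1-3. At 10% prevalence (OR 2-3), correlation rejects in 11%-29% within the arm and 20%-47% pooled. The Wald interaction then rejects in 0.7%-1.6%; it is conservative because an outcome cell is empty in 16%-39% of trials.

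**5. Power of the interaction test.** Take a 20-point benefit at one level and none at the other, 50% prevalence, placebo mortality 30%. On the risk-difference scale:

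- SE = √((0.21 + 0.09 + 0.21 + 0.21)/31) = 0.152.
- z = 0.20/0.152 = 1.31.
- Power ≈ Φ(1.31 − 1.96) = 26%.

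Simulated logistic Wald power is 22.3%, 26.9%, 23.4% and 21.4% at placebo mortality 25%, 30%, 40% and 50%. If the benefit is confined to a level with 10% prevalence, it is 0.3%-2.7%.

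**6. Multiplicity.** Item a and the three contrasts in item b make four tests. If independent, the chance of at least one false positive is 1 − 0.95⁴ = 18.5%.

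**The case against.** **Only under-specification.** If responsiveness is undefined, the plan cannot also be shown to use the wrong method: section 3.2 mentions placebo and treatment effects, so the authors may intend a comparison of arms. It is true that section 16.1 names neither an arm nor an outcome, so steps 3 and 4 test two possible readings, not a stated procedure. But no definition makes individual drug response observable in this design, and nothing commits the trial to a between-arm contrast by level. The mismatch remains.

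**The pooled figures flatter the concern.** Placebo patients cannot respond to vitamin C, so the within-arm reading is more natural. That is fair, and the 20%-57% range should lead.

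**Patients with neither extreme.** A reader might infer that item b drops patients with normal temperature or white cell count, since section 9.1 can admit them on heart rate plus respiratory rate, or on a qSOFA rise. The documents do not establish this. The item's heading covers presentation with or without an inflammatory response, and the list is not clearly exhaustive. The contrasts are ambiguous; exclusion is not shown.

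**Availability of values.** Nor does their place among the SIRS criteria prove that temperature and white cell count are recorded for everyone, because a patient can qualify without either.

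**Scale.** Section 16.2 speaks of a mortality difference, while a logistic interaction is a ratio of odds ratios. A constant 20-point benefit from 50% and from 25% gives odds ratios of (0.30/0.70)/(0.50/0.50) = 0.43 and (0.05/0.95)/(0.25/0.75) = 0.16. Arm-specific risks must therefore be reported beside the interaction.

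**Little gain.** Low power limits what the interaction can show. It does not make correlation a substitute, because the extra significant results answer a different question.

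**Conclusion.** The concern holds as a mismatch between question and method in a named aim. Responsiveness has no defined outcome, section 3.2 asks about effect modification, and no interaction is planned. A characteristic-outcome correlation cannot answer those questions, pooled or within one arm.

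The false-positive rates illustrate the size of the problem and do not predict this trial's results. They depend on an assumed odds ratio of 2-3, an assumed prevalence, death as the outcome, and a reading of the correlation that the plan does not spell out.

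The point should be settled before unblinding. It goes no further than Aim 3, which is third in order and carries no power claim. The primary mortality comparison is untouched.

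**What to change.** Replace the Aim 3 sentence in section 16.1 with:

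> For each clinical characteristic in section 3.2, Aim 3 items a and b, a logistic model for 28-day all-cause mortality (or another outcome the sponsor defines in advance) will include randomised treatment, the characteristic and their interaction, using both arms. Arm-specific risks by level and interaction estimates with 95% CI will be reported as exploratory, unadjusted for multiple tests.

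Add short definitions:

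- **Timing (item a).** Keep time to receipt continuous in both arms. State that it is undefined for anyone who never starts the infusion. Section 5.2 keeps consented patients who cannot start in time under data collection and does not say whether any are randomised.
- **Temperature and white cell count (item b).** Class the value at presentation as low, normal or high, so that patients with neither extreme have a level. State how a normal count with more than 10% bands is classed, since section 9.1 counts bands as a separate route to the criterion. Report how many patients lack a value.

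Penalised (Firth) likelihood is one reasonable choice for sparse cells. Repeating the models for mortality at ICU discharge, and a sensitivity analysis using time to randomisation if that time is recorded, are optional.

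The cost is a replaced passage and a few definitions. 28-day mortality is already collected. The drawback is the low power shown above, so Aim 3 should be described as hypothesis-generating, and a non-significant interaction should not be read as evidence of a uniform effect.

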17.0 Confidentiality

17.1 Data Security:

All standard confidentiality procedures will be observed for this study and all research staff will be trained on protocol and GCP standards before they will be allowed contact with participants or data. Any paper data, source or CRF or logs, will be kept in locked research offices. All University of Minnesota data protection policies will be reviewed and followed.

Electronic data will be entered into a REDCap™ database, which uses a MySQL database via secure web interface with data checks used during data entry to ensure data quality. REDCap™ includes a complete suite of features to support HIPAA compliance, including a full audit trail, user-based privileges, and integration with the institutional LDAP server. The MySQL database and the web server will both be hosted on the secure servers operated by the University of Minnesota Academic Health Center's Information Systems group (AHC-IS). The servers are in a physically secure location on campus and are backed up nightly, with the backups stored in accordance with the AHC-IS retention schedule of daily, weekly, and monthly tapes retained for 1 month, 3 months, and 6 months, respectively. Weekly backup tapes are stored offsite. The AHC-IS servers provide a stable, secure, well-maintained, and high-capacity data storage environment, and both REDCap™ and MySQL are widely-used, powerful, reliable, well-supported systems. Access to the study's data in REDCap™ will be restricted to the members of the study team by username and password.

Access to data exports will be limited with no member of staff given the ability to download full data sets; all exports will be limited to the "remove all tagged identifier fields" option when setting user rights. Additionally, all dates will be marked for date-shifting during the export process.

REDCap™ data files will be exported to shared drives housed under HIPAA-compliant AHC-IS servers on the MedDerm (\\med.ahc.umn.edu\med)(N:) shared drive.

Any other identifiable electronic data, including logs, will be stored on Box. Access to the study files on Box will be limited to those members of the study team.

Spreadsheets of data in aggregate form (summary statistics only, no individual data) will be electronically kept and may be electronically transmitted between study investigators only.

Documentation of research involvement will be recorded in the participant's medical record. Consents will not be placed in medical record.

18.0 Provisions to Monitor the Data to Ensure the Safety of Participants

18.1 Data Integrity Monitoring.

While there will be no planned full, interim data analysis, the PI will periodically review data for completeness and to ensure that all procedures are being followed as detailed in the protocol. The assigned Regulatory Specialist or CTSI monitor will also perform periodic quality assurance monitoring at any point requested by the PI or otherwise mandated by local policy.

18.2 Data Safety Monitoring.

Participants enrolled in this study will be monitored for adverse outcomes including adverse drug reactions, hospitalizations, and death. In addition, participants will be given contact information for the study team and will be counseled to report any adverse effects for duration of therapy. The Principal Investigator will oversee the safety of the study, including careful assessment and appropriate reporting of adverse events. All adverse and serious adverse events will be discussed with the PI within 48 hours for standard assessments (causality, expectedness, severity, and seriousness). IRB and other regulatory reporting requirements will be reviewed by study staff and followed with assistance of the Regulatory Specialist assigned to the study.

A Data Safety and Monitoring Board (DSMB) will be formed as a part of this study. Two physicians, with adequate clinical knowledge of the subject matter and research experience, along with one statistician will make up the DSMB. No member will have any affiliation with the study or data other than their responsibilities on the DSMB. Members will sign a Statement of Confidentiality.

DSMB members:

- [name] MPH: Associate Professor of Medicine, Division of Pulmonary, Allergy, Critical Care and Sleep Medicine, Department of Medicine
- [name]: Professor, Department of Surgery
- [name]: Assistant Professor, Division of Biostatistics, School of Public Health

Safety Data Collection:

All adverse events will be collected with particular attention paid towards those listed as most frequent risks of Vitamin C, including nausea, vomiting, headaches, stomach cramps, and headaches. Adverse events will be collected on case report forms as completed within REDCap™. Three different types of events will be differentiated: those expected and/or related to study drug, those expected and/or related to any other research procedure, and those expected

PROTOCOL TITLE: Evaluating Vitamin C in Septic Shock: A Randomized Double Blind Control Trial

VERSION DATE: March 17, 2020

and/or related to underlying septic shock condition. All safety data will be collected from the time of consent to the final 28 day chart review visit. All events will be followed until either resolution or 30 days-post last study visit, whichever comes first.

Mortality Data Review:

All mortality data will be collected when site becomes aware of death. This could happen while participant is still in hospital or during the 28-day final chart review or at any other time point. All deaths will be reviewed by PI and Regulatory Specialist for IRB prompt reporting guidelines.

Information Provided to DSMB

Reports to DSMB will be prepared in coordination with an independent statistician from BDAC. Data provided includes:

- Cumulative
 - Safety data (including adverse events)
 - Primary outcome data for Specific Aim 1 (mortality data)
 - Primary outcome data for Specific Aim 2 (clinical endpoints)
- Since last DSMB meeting
 - Relevant IRB submissions, including Reportable New Information and Modifications
 - Monitoring reports

DSMB Meeting Schedule

- 6 Months Post First Randomization
 - All data will be sent to DSMB.
 - Case report forms and paper documents, including consents, will be reviewed by Regulatory Specialist or CTSI monitor. Monitoring reports will be made available to DSMB.
- Annually Post First Randomization
 - All data will be sent to DSMB.
 - Case report forms and paper documents, including consents, will be reviewed by Regulatory Specialist or CTSI monitor. Monitoring reports will be made available to DSMB.

DSMB Meeting Components

The DSMB members will be provided with data reports before the meeting date, with sufficient time to allow for review. Reports and all necessary information will be electronically provided to DSMB members through email. DSMB members will meet either in-person or telephonically/electronically as necessary to allow for clinical schedule restraints. The Regulatory Specialist will attend all DSMB meetings to compile minutes. This individual will also prepare all DSMB Summaries.

DSMB IRB Reporting

All DSMB Summaries will be submitted to the IRB per local guidelines.

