23.0 Multi-Site Research

This is a multi-site study that will have a phased rollout at Fairview Hospitals and HealthEast Hospitals.

1. Fairview Southdale ICU: this will be the pilot site and the study will be started at this location first. The PI is the director of the ICU at this location.
2. Fairview UMMC ICU (includes MICU and SICU) and Ridges ICU: these sites will be secondary sites and will be initiated after Southdale.
3. HealthEast St. Joseph's Hospital ICU: this site will be last and require additional IRB approval from the local human ethics board. This site will only be initiated if additional recruitment is necessary. If and when the site is initiated and receives IRB approval, those documents would be submitted to the UMN IRB, if necessary.

4. Essentia Health: this site will require additional IRB approval from the local IRB. This site will be initiated once local-IRB is secured.

23.1 Study-Wide Number of Participants:

140 participants.

23.2 Study-Wide Recruitment Methods:

Each local site will rely on internal study clinicians and floor staff to identify candidates for the study.

23.3 Study-Wide Recruitment Materials:

Not applicable. No recruitment materials.

23.4 Communication Among Sites:

The study will employ a lead Regulatory Specialist who will coordinate all communication and regulatory efforts. Box will be utilized to manage study-wide documents so that team members can easily obtain the most current version of all documents. The Regulatory Specialist will manage IRB reporting at all sites and will work with the PI to ensure all non-compliance, adverse events, and other reportable events are reviewed and reported in accordance with local policies. There will be three IRBs involved, UMN, HealthEast, and Essentia Health.

All study data will be entered into REDCap™ with each site being assigned a specific group so that staff at one site cannot see participant data from another site.

23.5 Communication to Sites:

The PI, the Project Manager, and the Regulatory Specialist will work together to release site-wide communications. As the study begins enrollment at each new site, it is expected to have semi-often meetings (telephone or in-person) to ensure an efficient and appropriate start-up.

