24.0 Resources Available

24.1 Resources Available:

This study will include a PI, several co-investigators, project manager, coordinator, and a regulatory specialist. Bedside nursing will be used to assist PI with clinical assessments as necessary and as available. In the case of any medical or psychological event, clinical staff will be immediately available for assessment or treatment.

All staff will be trained on research procedures before being allowed access to participants or data. All training will be documented within the regulatory binder and reviewed by the PI and project manager.

As this study will involve staff at several sites, the Project Manager and the Regulatory Specialist will coordinate training efforts as required by each site.

This study will take place at Fairview Southdale, UMMC, Ridges, HealthEast St. Joseph's and Essentia Health in Duluth.

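### A study-team member attends every DSMB meeting and writes its Summaries with no closed session, so any by-arm interim results shown there would be open to the operational team

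*Combined protocol and SAP*

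**What the plan says.** Three sets of statements bear on this point.

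- **Attendance and authorship (Section 18.2, DSMB Meeting Components).** "The Regulatory Specialist will attend all DSMB meetings to compile minutes", followed by "This individual will also prepare all DSMB Summaries". No meeting or part of a meeting is excepted. The Summaries then go to the IRB.
- **What the DSMB receives (Section 18.2, Information Provided to DSMB).** Reports are prepared with an independent statistician. They contain cumulative safety data, mortality (the Aim 1 outcome) and the Aim 2 clinical endpoints. Whether these are shown by arm or pooled is not stated.
- **Who the Regulatory Specialist is.** Section 24.1: "This study will include a PI, several co-investigators, project manager, coordinator, and a regulatory specialist". Section 23.4: "The study will employ a lead Regulatory Specialist who will coordinate all communication and regulatory efforts"; the same section has the role manage IRB reporting at all sites and work with the PI on adverse events. Section 23.5: "The PI, the Project Manager, and the Regulatory Specialist will work together to release site-wide communications". Section 18.2, Mortality Data Review: "All deaths will be reviewed by PI and Regulatory Specialist for IRB prompt reporting guidelines".

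Section 18.2 also requires that DSMB members have no other tie to the study or its data, and that they sign a confidentiality statement. It asks nothing similar of the person who takes the minutes.

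**The concern.** The protocol takes care to make the DSMB independent of the trial, then seats a member of the trial's staff in all its meetings and has that person write what comes out of them. In a double-blind trial, comparative interim results are normally kept from those who run it, because such knowledge can influence decisions that are still open.

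Several are open here. The covariates of the mortality model are left to the investigators or to baseline differences (Section 16.1). The secondary endpoints are provisional, subject to power and enrolment (Section 3.2). One site opens only if recruitment needs it (Section 23.0). If the team could have known the direction of the mortality difference, a reader could not tell whether these choices were made independently of it.

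**Working it through.** There is no figure to reproduce. The check compares roles and data flow across sections.

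1. **Is the role on the study team?** Yes. Section 24.1 lists it beside the PI and coordinator, and Sections 23.4 and 23.5 give it cross-site and PI-facing duties. Section 23.4 speaks of a lead Regulatory Specialist and Section 18.2 simply of the Regulatory Specialist. One role is the plain reading, supported by the singular in Section 24.1, but a second person is not excluded.
2. **Does the role have a stated unblinded function?** No. Section 4.2 gives randomization and blinding to Investigational Drug Services and the research pharmacist.
3. **Is any part of a DSMB meeting closed to it?** None is described. There is also no separate set of closed minutes and no limit on what a Summary may contain.
4. **How many meetings fall during enrolment?** Section 18.2 sets meetings at 6 months and annually after first randomization, so at 6, 12 and 24 months. Section 8.0 expects enrolment to take up to 1.5 years, or 1.5 × 12 = 18 months. Two meetings (6 and 12 months) precede that date, taking enrolment to run from about the first randomization.
5. **What would the role learn that it does not already know?** This depends on the display, which is not stated:

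| DSMB report | New information for the Regulatory Specialist | Consequence |
|---|---|---|
| Pooled | Little. The study team has REDCap access (17.1), the regulatory specialist reviews REDCap data (16.3), and deaths already come to this role (18.2) | Added exposure small |
| By arm, labelled or coded | Comparative mortality and clinical results | Interim confidentiality depends on one person's discretion, with no written safeguard |

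6. **Which display is more likely?** Involving an independent statistician suggests by-arm reports, and a DSMB shown only pooled data could not compare harm between arms. On the other side, Section 18.1 says no full interim analysis is planned. Neither settles the matter.
7. **Would by-arm totals reveal who received Vitamin C?** Not by themselves. Aggregate results carry no participant-level allocation, and under Section 13.1 unblinding for care is arranged with the pharmacy.

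**The case against.** The strongest reply is that only attendance and authorship are stated. A leak needs two further facts: that by-arm results are shown or discussed while the Regulatory Specialist is present, and that the specialist passes them on. The documents establish neither. Reports are sent to DSMB members, and the specialist is not named as a recipient. The only stated destination of the Summaries is the IRB. The role has no bedside duties, and site communications are issued jointly, not by this role alone.

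The routes to bias are also narrow. Both primary endpoints are all-cause mortality (Section 3.1), so there is no cause of death to classify, and the unadjusted chi-square comparison is already named. The joint review of deaths serves IRB reporting; it is not endpoint adjudication.

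Most of this stands, and it rules out three stronger readings that a reader might infer:

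- *That every DSMB meeting exposes comparative data.* By-arm display is not stated.
- *That the trial could not show its blind held.* Participant-level allocation stays with the pharmacy, and aggregate results would not disclose it.
- *That the death review lets this role influence the primary outcome.* Its stated purpose is regulatory.

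The reply does not remove the attendance rule itself. That rule is written without exception, covers a person with daily operational links to the PI, and comes with no safeguard should by-arm data be presented.

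**Conclusion.** The point holds in conditional form and is minor. The protocol leaves a route by which interim comparative results could reach the operational team. It does not show that they will. The conclusion rests on two assumptions: that the Regulatory Specialist in Sections 18.2, 23 and 24.1 is the same role, and, for the risk to be material, that DSMB reports are shown by arm. If reports are always pooled, little is added to what the team already sees.

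The documents give no basis for a numerical estimate of bias. What is at stake is confidence that the remaining analysis and conduct decisions were made without knowledge of the treatment comparison.

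**What to change.** Amend the DSMB text in Section 18.2 to:

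- state whether reports are pooled or by arm;
- divide each meeting into an open session with pooled data, which the Regulatory Specialist attends and minutes, and a closed session for any by-arm review, which the specialist does not attend;
- have a DSMB member minute the closed session, or the independent statistician if that person attends, and restrict by-arm reports and closed minutes to those people;
- limit the Summary that goes to the study team and IRB to the recommendation, without comparative data.

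The cost is a short text change and a small added minuting duty. The protocol has the independent statistician help prepare reports but does not say that this person attends meetings, so the duty may fall to a DSMB member. No new post is needed.
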